4.2.2 Safety Population

The primary analysis set for safety analyses will include subjects who received at least one dose of study drug.

On treatment data will be analyzed and defined as data collected from the first dose of study drug through the date of last dose of study drug plus 30 days.

4.3 Data Handling Conventions

Missing data can have an impact upon the interpretation of the trial data. Other than the endpoints discussed below, values for missing data will not be imputed.

For the analysis of post-baseline categorical efficacy endpoints, if a data point is missing and is preceded and followed in time by values that are deemed successes, then the missing data point will be termed a success; otherwise the data point will be termed a failure.

Any subject with missing data due to premature discontinuation of the study medication will be considered a failure at the time points on, or following, the date of discontinuation. If no HCV RNA values are obtained after the last dose of study medication, the subject will be considered a treatment failure for the SVR endpoints.

Where appropriate, safety data for subjects that did not complete the study will be included in summary statistics. For example,

- If a subject received study medication, the subject will be included in a summary of adverse events according to the treatment received; otherwise, if the subject is not dosed then they will be excluded from the summary.
- If safety laboratory results for a subject are missing for any reason at a time point, the subject will be excluded from the calculation of summary statistics for that time point. If the subject is missing a pre-dose value, then the subject will be excluded from the calculation of summary statistics for the pre-dose value and the change from pre-dose values.

Values for missing vital signs data will not be imputed; however, a missing Day 0 result will be replaced with a screening result, if available.

4.4 Efficacy Analyses

4.4.1 Primary Analysis

The primary efficacy endpoint is SVR₁₂ (HCV RNA <LLOQ 12 weeks after cessation of therapy.)

There is no active comparator group for this study (as in most clinical trials with all oral therapies in these populations).

In the primary efficacy analysis, an exact Clopper-Pearson 95% confidence interval will be computed for the SVR₁₂ rate.

The primary analysis will be performed after all enrolled subjects have been followed through 12 weeks post-treatment or discontinued from study.

4.4.2 Secondary Analysis

The proportion of subjects with HCV RNA below the LLOQ over time (including SVR endpoints) will be presented.

Descriptive summaries and listings will be provided for additional efficacy evaluations of the proportion of subjects who experience virologic failure and other endpoints of interest including ALT normalization, plasma HCV RNA actual values, and change from baseline. Heterogeneity among the study populations (pre- versus post-transplant, severity of liver disease, type of ARVs, baseline characteristics and others) and limited sample size will preclude us from performing extensive multivariate models to determine predictors of treatment success or failure.

Exploratory regression analyses may be performed to assess the relationship between demographic, baseline characteristics, (including baseline viral load, genotype, age, sex, race, ethnicity, presence/absence of cirrhosis, baseline ALT level, prior treatment experience, response to previous treatment [if applicable], and BMI) and antiviral activity (as measured by HCV RNA log reduction).

Details on efficacy analyses will be described in the statistical analysis plan.

4.5 Safety Analysis

Safety will be evaluated by assessment of clinical laboratory tests, physical examinations, and vital signs measurements at various time points during the study, as well as the documentation of AEs.

5 PATIENT POPULATIONS

5.1 Retrospective Arm Inclusion Criteria

The intent of the Retrospective Arm is to capture all HIV/HCV coinfected patients exposed to sofosbuvir based DAA therapy since 2014, to mirror the population enrolled in the Prospective Arm.

Liver transplant candidates (listed) and decompensated cirrhotics (not listed) for liver transplant

1. Treated with sofosbuvir based DAA for any duration since 2014
2. Age >18 years at time of treatment
3. Pre-treatment Child's Pugh score of 7 or greater
4. Pre-treatment laboratory MELD ≥ 6 and ≤ 30
5. Survived at least 12 weeks after start of treatment
6. HIV-positive on stable ART for at least 4 weeks pre-treatment
7. Chronic HCV infection with at least one measurement of plasma HCV RNA $\geq 1,000$ IU/mL prior to treatment with sofosbuvir based DAA therapy
8. HCV genotype 1, 4, 5 or 6

Liver transplant recipients

1. Treated with sofosbuvir based DAA post liver transplant for any duration since 2014
2. Liver transplant from 2000 to current
3. Age >18 years at time of treatment
4. Treated initiated at least 1 month post-liver transplant
5. Post-LT stage of liver disease documented within the prior year of treatment start date by standard of care methods of liver staging
6. Survived at least 12 weeks after start of treatment

7. HIV-positive on stable ART for at least 4 weeks pre-treatment
8. Chronic HCV infection with at least one measurement of plasma HCV RNA $\geq 1,000$ IU/mL prior to treatment with sofosbuvir based DAA therapy
9. Fibrosis staging done within 1 year of start of DAA therapy
10. HCV genotype 1, 4, 5 or 6

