3.0 STUDY DESCRIPTION

Approximately fifty HIV/HCV coinfecte patients with decompensated liver disease will be enrolled in the study. Ten (up to twenty) subjects will be treated with FDC SOF/LDV pre or post liver transplant and followed prospectively. Forty + subjects will be enrolled retrospectively with the intent to capture all patients who have been exposed to sofosbuvir based DAA therapies at participating sites since 1/2014, and to mirror the population being enrolled prospectively.

In addition, participants in the retrospective arm will be contacted to consent to one prospective study visit for liver staging to determine rates of reversal of decompensation, reversal of cirrhosis and improvements in graft survival post treatment, and for future contact by the NIH Clinical Center to assess longer term outcomes when this study ends.

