3.1 Retrospective Arm

Participating sites will collect clinical data on all of the HIV/HCV co-infected patients with decompensated liver disease (CPT >7 pre or post liver transplant) treated with sofosbuvir based DAA therapies since 1/2014 at their center. This will be done under IRB approved waiver of consent if possible so that all treated patients meeting the inclusion criteria can be included to avoid statistical bias. Data collected will mirror the data collected in the prospective arm. In addition, participants will be contacted to provide consent to return to the site for one visit for current liver staging to evaluate reversal of fibrosis (unless liver staging by Fibroscan or liver biopsy was done in the previous 12 months), and to be contacted in the future by the NIH Clinical Center for long term follow-up.

- Efficacy will be defined as HCV RNA undetectable \geq 12 weeks post end of sofosbuvir based DAA therapy.
- Safety and tolerability will be defined by
 - discontinuation rates
 - rates of hospitalization during DAA therapy
 - frequency of anemia requiring blood transfusion or EPO
 - survival.
- Reversal of decompensation: defined by CP score and MELD score at last follow-up (evaluated at time to event given the variability in length of follow-up post treatment)
- Reversal of fibrosis: defined by liver fibrosis by Fibroscan or biopsy at last follow-up (evaluated at time to event given the variability in length of follow-up post treatment)

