5.2 Prospective Arm Inclusion/Exclusion Criteria

Pre-liver transplant candidates

- Enrollment will be targeted to occur at least 12 weeks prior to anticipated transplant date.
- Screening laboratory MELD ≥ 6 and ≤ 20 (NIH) or ≤ 30 (non-NIH sites)

Post-liver transplant recipients

- Recipients with evidence of recurrent HCV viremia
- Subjects with compensated and decompensated liver disease
- Screening laboratory MELD ≥ 6 and ≤ 20 (NIH) or ≤ 30 (non-NIH sites)
- Life expectation of >12 weeks

Inclusion Criteria

1. Over 18 years of age at screening
2. Female participants of child bearing potential must have a negative urine pregnancy test at day 0 prior to dosing.
3. Has received a liver transplant for HCV or has decompensated cirrhosis (Child's Pugh score of 7 or greater)
4. Have HIV-1 infection and either:
 - a) On HIV medications (antiretrovirals) for at least 4 weeks WITH
 - An HIV viral load less than the level of detection OR
 - b) On no HIV medications for at least 8 weeks WITH:
 - A CD4 count of 500 cells/mm³ or more OR
 - HIV viral load of < 500 copies/mL with a stable CD4 count for at least 3 months
5. Chronic HCV infection as documented by at least one measurement of plasma HCV RNA $\geq 1,000$ IU/mL during screening and at least one of the following:
A positive anti-HCV antibody, HCV RNA, or an HCV genotype test at least 12 months prior to baseline (Day 0) visit together with positive HCV RNA test
6. HCV genotype 1, 4, 5 or 6
7. The use of an anti-HCV positive donor is allowed for participants who have detectable HCV RNA at the time of transplant.
8. The use of an HIV+ donor is allowed if the participant is enrolled in an IRB approved HOPE Act protocol at the transplant site. If the HIV+ donor is also HCV co-infected, then the recipient must have detectable HCV RNA at the time of transplant.
9. Able to effectively communicate with the Investigator and other center personnel.
10. Willing to give written informed consent and comply with the study restrictions and requirements.
11. Willingness to allow stored blood or tissue samples to be used in the future for studying liver

disease and immune function.

12. Willingness to permit HLA typing to be performed.
13. Have a transplant team available for all primary and transplant-related care.
14. If not yet transplanted: expected to be at least 12 weeks prior to transplant in order to complete treatment course.

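### The retrospective arm admits only patients who survived 12 weeks from treatment start, so early deaths are removed from its SVR12, safety and survival results by design

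*Combined protocol and SAP*

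**What the plan says.** Section 5.1 gives two eligibility lists for the retrospective arm, one for transplant candidates and decompensated cirrhotics and one for transplant recipients. Both contain "Survived at least 12 weeks after start of treatment" (item 5 and item 6 respectively).

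The surrounding text points the other way:

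- Section 5.1 opens with "The intent of the Retrospective Arm is to capture all HIV/HCV coinfected patients exposed to sofosbuvir based DAA therapy since 2014" and says the arm should mirror the prospective population. Its first item for candidates is "Treated with sofosbuvir based DAA for any duration since 2014", so a short course is no bar to entry.
- Section 3.1 justifies the waiver of consent "so that all treated patients meeting the inclusion criteria can be included to avoid statistical bias". It lists survival among the arm's safety and tolerability measures, with discontinuation, hospitalisation during therapy, and anaemia needing transfusion or EPO. Section 10.6 asks sites to record historical deaths.
- Sections 4.2.1 and 4.2.2 analyse everyone who received at least one dose. Under Section 4.3, a patient with no HCV RNA value after the last dose is handled as follows: "the subject will be considered a treatment failure for the SVR endpoints".
- The nearest prospective condition, in Section 5.2, is "Life expectation of >12 weeks", listed for post-transplant recipients only.

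On size, Section 3.0 states "Forty + subjects will be enrolled retrospectively with the intent to capture all patients who have been exposed" and "Ten (up to twenty) subjects will be treated with FDC SOF/LDV pre or post liver transplant and followed prospectively".

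**The concern.** Whether a patient survived 12 weeks is known only after treatment has begun. Using it as an entry condition means a patient treated in 2014 who died in week 6 is never abstracted. The 12 weeks cover the whole of a 12-week course and half of a 24-week course, so for a 12-week course no on-treatment death can appear in this arm at all.

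Three sets of results are affected. SVR12 loses patients who would have been failures. Survival starts with 12 weeks of guaranteed time. The on-treatment safety measures lose whatever hospitalisations, transfusions and discontinuations preceded those deaths. The candidates in this arm have a Child-Pugh score of 7 or more and a MELD score up to 30, so early death is plausible. Any estimate that combines the arms mixes one that counts early deaths with one that cannot contain any.

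**Working it through.** **Inputs.** Retrospective n = 40 and prospective n = 10 (up to 20), from Section 3.0; total n = 50 and Tables 1 and 2, from Section 4.1; exact Clopper-Pearson 95% interval, from Section 4.4.1; failure rule, from Section 4.3. The number of deaths within 12 weeks of treatment start is not in the documents. **Assumption:** k = 1 to 7 deaths excluded around 40 retained patients, that is k/(40 + k) = 1/41 = 2.4% up to 7/47 = 14.9% of those treated. The observed success counts below (36/40, 46/50) are illustrations; 46/50 is 36/40 plus an assumed 10/10 in the prospective arm.

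**Step 1: reproduce the plan's figures.** With x successes in n, the limits are the beta quantiles B(0.025; x, n − x + 1) and B(0.975; x + 1, n − x); when x = n the upper limit is 1. For n = 50 this gives 0.929–1 (50/50), 0.863–0.995 (48/50) and 0.808–0.978 (46/50), and all six Table 1 intervals match. For Table 2, 1 − (1 − p)^50 gives 39.5%, 92.3%, 99.5% and 99.97%, which agrees with the printed values. Both tables treat all 50 patients as able to show any failure or event.

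**Step 2: restore the excluded deaths.** Each is a failure under Section 4.3, so x/n becomes x/(n + k).

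| Deaths excluded (k) | Retrospective SVR12 (95% CI) | Pooled SVR12 (95% CI) |
|---|---|---|
| 0 | 36/40 = 90.0% (76.3–97.2) | 46/50 = 92.0% (80.8–97.8) |
| 1 | 36/41 = 87.8% (73.8–95.9) | 46/51 = 90.2% (78.6–96.7) |
| 2 | 36/42 = 85.7% (71.5–94.6) | 46/52 = 88.5% (76.6–95.6) |
| 4 | 36/44 = 81.8% (67.3–91.8) | 46/54 = 85.2% (72.9–93.4) |
| 7 | 36/47 = 76.6% (62.0–87.7) | 46/57 = 80.7% (68–90) |

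**Step 3: the same effect as a rate.** If SVR12 among 12-week survivors is s and 12-week mortality is q, SVR12 among all treated is s(1 − q). With s = 95% (assumed) and q = 2%, 5% and 10%, this is 93.1%, 90.3% and 85.5%.

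**Step 4: safety information on early death.** Retrospective patients have zero probability of showing death within 12 weeks, so only the 10 to 20 prospective patients are informative. At a true risk of 5%, the chance of seeing at least one such death is 1 − 0.95^10 = 40% to 1 − 0.95^20 = 64%. Table 2 gives 92% for 50 patients.

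**Step 5: does the condition serve another purpose?** SVR12 is assessed 12 + 12 = 24 weeks after the start of a 12-week course and 24 + 12 = 36 weeks after the start of a 24-week course. Survival to week 12 therefore does not make a patient evaluable for SVR12, and Section 4.3 already classifies patients without post-treatment HCV RNA.

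**The case against.** The case on the other side has five parts.

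- **Pooling is inferred.** Section 4.1 speaks of combining pre- and post-transplant patients, not the two arms; Section 3.1 gives the retrospective arm its own efficacy and safety definitions; and the analysis populations refer to study drug, which Section 8 describes for the prospective arm. This is fair as to wording. But the n = 50 behind Tables 1 and 2 can only be reached by adding 10 prospective and 40 retrospective patients, so pooling is the natural reading. The retrospective result is affected on its own in any case.
- **The waiver text is limited to patients meeting the inclusion criteria.** That is so, and the waiver still removes selection by ability to consent. It cannot remove the selection that the criteria themselves impose, and the conflict with the aim of capturing all exposed patients remains.
- **The size is unknown.** This stands. With no early deaths the bias is zero, and the upper end of the assumed range has no source. The loss of hospitalisation, anaemia and discontinuation events also lowers those rates only if patients who died early had more of them, which is plausible but not shown.
- **Later deaths are kept, and part of the arm's purpose is follow-up of cured patients.** This also stands. The damage is greatest for SVR12 and early safety.
- **The prospective arm screens out some high-risk patients at baseline** (haemoglobin, eGFR, sodium, active infection), and the retrospective lists do not. Deleting the survival condition therefore leaves the arms different. That difference should be handled with baseline variables; it does not justify selecting on survival.

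The study has no comparator and calls itself a pilot. That lowers the formal stakes, but the estimates are its whole product.

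**Conclusion.** The concern holds. The condition is in the current text of both lists, and nothing elsewhere counts the patients it removes, labels the results as conditional on survival, or plans an all-treated analysis. The prospective life-expectation item is not equivalent: it is a judgement at entry, for recipients only, and a patient who then dies stays in the analysis.

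Twelve-week survival in the retrospective arm is 100% by construction. If any treated patient died in that window, SVR12 and survival are too high. Each excluded death takes roughly 2 percentage points off a retrospective 36/40 and a little under 2 points off a pooled 46/50. The totals in the table rest on the assumed 1 to 7 deaths and the assumed success counts. The direction does not depend on those assumptions; the size does. This must be fixed before abstraction is closed, because patients screened out at entry cannot be recovered by any later analysis.

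**What to change.** 1. Delete the 12-week survival condition from both lists in Section 5.1. Include every patient who took at least one dose of sofosbuvir-based DAA and met the baseline criteria, and state in Section 4.2 that study drug means that therapy for the retrospective arm.
2. State in Section 4.3 that death before the SVR12 assessment is a failure in both arms. Measure survival and the other safety measures from Day 0.
3. To address baseline differences between the arms, add a sensitivity analysis restricted by Day 0 values to the prospective arm's laboratory limits. Haemoglobin, sodium and creatinine are already recorded at Day 0 under Section 11.2.
4. If a site cannot retrieve its early deaths, label its results as conditional on 12-week survival and keep them out of the primary estimate. Report how many sites and patients this affects, since leaving sites out is itself a form of selection.

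The cost is a protocol amendment and chart abstraction for a handful of extra patients under the same consent waiver. The SVR12 and survival figures may become less favourable.

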5.2 Prospective Arm Inclusion/Exclusion Criteria

Pre-liver transplant candidates

- Enrollment will be targeted to occur at least 12 weeks prior to anticipated transplant date.
- Screening laboratory MELD ≥ 6 and ≤ 20 (NIH) or ≤ 30 (non-NIH sites)

Post-liver transplant recipients

- Recipients with evidence of recurrent HCV viremia
- Subjects with compensated and decompensated liver disease
- Screening laboratory MELD ≥ 6 and ≤ 20 (NIH) or ≤ 30 (non-NIH sites)
- Life expectation of >12 weeks

Inclusion Criteria

1. Over 18 years of age at screening
2. Female participants of child bearing potential must have a negative urine pregnancy test at day 0 prior to dosing.
3. Has received a liver transplant for HCV or has decompensated cirrhosis (Child's Pugh score of 7 or greater)
4. Have HIV-1 infection and either:
 - a) On HIV medications (antiretrovirals) for at least 4 weeks WITH
 - An HIV viral load less than the level of detection OR
 - b) On no HIV medications for at least 8 weeks WITH:
 - A CD4 count of 500 cells/mm³ or more OR
 - HIV viral load of < 500 copies/mL with a stable CD4 count for at least 3 months
5. Chronic HCV infection as documented by at least one measurement of plasma HCV RNA $\geq 1,000$ IU/mL during screening and at least one of the following:
A positive anti-HCV antibody, HCV RNA, or an HCV genotype test at least 12 months prior to baseline (Day 0) visit together with positive HCV RNA test
6. HCV genotype 1, 4, 5 or 6
7. The use of an anti-HCV positive donor is allowed for participants who have detectable HCV RNA at the time of transplant.
8. The use of an HIV+ donor is allowed if the participant is enrolled in an IRB approved HOPE Act protocol at the transplant site. If the HIV+ donor is also HCV co-infected, then the recipient must have detectable HCV RNA at the time of transplant.
9. Able to effectively communicate with the Investigator and other center personnel.
10. Willing to give written informed consent and comply with the study restrictions and requirements.
11. Willingness to allow stored blood or tissue samples to be used in the future for studying liver

disease and immune function.

12. Willingness to permit HLA typing to be performed.
13. Have a transplant team available for all primary and transplant-related care.
14. If not yet transplanted: expected to be at least 12 weeks prior to transplant in order to complete treatment course.
15. If not yet transplanted: Must have prior standard of care liver staging consistent with F4.
16. If not yet transplanted: For pre-LT patients with HCC, they must meet Milan criteria at time of enrollment to be eligible
17. If post-liver transplant, must be at least 1 month since transplant procedure to begin treatment.
18. If post-liver transplant, liver disease staging must be documented within the prior year by standard of care methods of liver staging

Exclusion Criteria

1. Positive HBsAg or anti-HBc at screening.
2. History of any other clinically active chronic liver disease (e.g., hemochromatosis, autoimmune hepatitis, Wilson's disease, ≥ 1 -antitrypsin deficiency, alcoholic liver disease, and toxin exposures).
3. Treatment with unlicensed herbal/natural remedies suggested to be taken for hepatitis treatment, such as Milk thistle, St. Johns Wort or Cats Claw, within 28 days of start of treatment
4. Treatment with IFN, RBV, telaprevir or boceprevir or any other approved or experimental medication with known anti-HCV activity within 1 month prior to screening date
5. Any prior exposure to an HCV NS5a specific inhibitor
6. A personal history of or first degree relative with a history of Torsade de pointes.
7. Abnormal hematological and biochemical parameters, including:
 - a. Hemoglobin < 8 g/dL
 - b. Estimated GFR, calculated by the CKD-EPI equation, < 30 mL/min/ per 1.73 m²
 - c. Sodium < 120 mmol/L
8. History of major organ transplantation other than liver or kidney transplantation.
9. Difficulty with blood collection/poor venous access for phlebotomy that would prevent the collection of study required samples
10. Infection requiring systemic antibiotics at the time of screening
11. Active or recent history (≤ 6 months) of drug or alcohol abuse
12. Gastrointestinal disorder or post-operative condition that could interfere with the absorption of the study drug.
13. Donation or loss of more than 400 mL blood within 8 weeks prior to first dose administration.
14. Any medications prohibited (see table 2 in section 8.11) within 28 days prior to Day 0 visit and likely required during study treatment period
15. History of clinically significant drug allergy to nucleoside/nucleotide analogs.

16. History or current evidence of psychiatric illness, endocrine, immunologic disorder, pulmonary, cardiac disease, seizure disorder, cancer or other conditions that in the opinion of the investigator makes the patient unsuitable for the study. Chronic medical conditions, especially if treated with medications (such as hypertension), must be stable at the time of screening. No new therapies should be started within 28 days prior to the study that may confound the assessment of study drug safety.
17. Participation in a clinical study (other than an IRB approved HOPE Act protocol involving the utilization of an HIV+ donor) in which an investigational drug, biologic, or device was received within 12 weeks prior to first dose administration.
18. Pregnant/Breastfeeding women

